8.10.1.2.1 Proportion of Patients Requiring no Platelet Transfusion During the Study

The number and proportion of patients who required no platelet transfusion during the study will be calculated by treatment group. The proportion of patients who required no platelet transfusion in the S-888711 group will be compared with that in the placebo group using the Cochran-Mantel-Haenszel test adjusted by the stratification factors.

8.10.1.2.2 Proportion of Responder Rate

The number and proportion of patients who meet the criteria for a responder at least once during the study (ie, 'Responders') will be calculated for each treatment group. The responder rate in the S-888711 group will be compared with that in the placebo group using the Cochran-Mantel-Haenszel test, with consideration of stratification factors.

The number and proportion of 'Responders' will be calculated at each scheduled time point.

8.10.1.2.3 Duration of the Increase in Platelet Count

Median and quartiles for the duration of increased platelet count will be calculated in each treatment group with or without platelet transfusions. The duration will be compared between the S-888711 group and placebo group using Wilcoxon rank sum test.

8.10.1.2.4 Proportion of Patients who Required Rescue Therapy

The number and proportion of patients who required rescue therapy will be calculated for each treatment group.

8.10.1.2.5 Frequency of Platelet Transfusion and Dose (Unit) Transfused During the Study

Summary statistics for the number and dose (unit) of platelet transfusions during the study will be calculated for patients who received a platelet transfusion.

8.10.1.2.6 Time Course of Platelet Count

Summary statistics for platelet count will be calculated at each scheduled time point in each treatment group. Summary statistics for the change in platelet count from baseline will also be calculated.

Summary statistics for the maximum platelet count and the maximum change in platelet count of each patient will be calculated by treatment group.

8.11 Safety Analyses

Safety analyses will be performed for the safety population.

8.11.1 Adverse Events

AEs will be classified by system organ class and preferred term using the Medical Dictionary for Regulatory Activities (MedDRA) Version 18.0 or higher. Of the AEs reported on the CRF, TEAEs will be used for the analyses of safety. The definition of a TEAE is provided in Section 7.8.2.

The number of patients who experience at least 1 TEAE, death, other treatment-emergent SAEs, significant TEAEs, and TEAEs leading to withdrawal will be counted for each treatment group. The number of TEAEs, counted by cases reported, will also be presented. Treatment-related TEAEs will be summarised in the same manner as the overall summary of TEAEs.

A summary of TEAE by MedDRA system organ class and preferred term will be presented for each treatment group, including the percentage of patients. The summary of TEAEs by severity will also be presented by system organ class and preferred term.

The number and proportion of patients who experience bleeding-related TEAEs will be calculated by treatment group. Bleeding-related TEAEs are defined as TEAEs which were classified as “haemorrhage terms (except laboratory terms)” using Standard MedDRA Queries (SMQ).

8.11.2 Adverse Events of Special Interest

- Thrombotic/thromboembolic complications

The number and percentage of patients who have a thrombotic/thromboembolic AE or that may have the potential to be classified as a thrombotic/thromboembolic AE will be summarised by treatment group. Thrombotic/thromboembolic AEs include, but are not limited to, portal vein thrombosis and mesenteric vein thrombosis. The definition of thrombotic/thromboembolic AEs is described as AEs which are classified as follows using the SMQ: “embolic and thrombotic events, arterial”, “embolic and thrombotic events, venous”, or “embolic and thrombotic events, vessel type unspecified and mixed arterial and venous”.

8.11.3 Vital Signs

Summary statistics for vital signs, measured after randomisation, and their changes from baseline will be calculated at each scheduled time point by treatment group. Baseline will be the value obtained on Day 1 (before initiation of study medication). If the value on Day 1 is missing and the value obtained before randomisation was obtained within 7 days of initiation of study medication, that value can be used as a baseline measurement.

8.11.4 Laboratory Tests

Summary statistics for laboratory tests, measured after randomisation, and their changes

from baseline will be calculated at each scheduled time point by treatment group. Baseline will be the value obtained on Day 1 (before initiation of study medication). If the value on Day 1 is missing and the value obtained before randomisation was obtained within 7 days of initiation of study medication, that value can be used as a baseline measurement.

8.11.5 **Electrocardiogram**

The number and proportion of patients with an abnormal ECG finding will be calculated at each scheduled time point.

8.11.6 **Portal Vein Thrombosis**

The number and proportion of patients who experienced portal vein thrombosis will be counted.

8.11.7 **Portal Blood Flow**

Summary statistics by category for the direction of portal blood flow (ie, hepatofugal, hepatopetal, stasis) will be counted for patients who underwent Doppler ultrasonography at each scheduled time point.

8.12 **Pharmacokinetic Analysis**

Plasma S-888711 concentrations will be listed by nominal sampling time and sampling design group (intensive PK sampling or sparse PK sampling). Plasma S-888711 concentrations for patients who completed at least 5 days of study drug administration will be summarised by nominal sampling time and sampling design group. Summary statistics will include the number of non-missing observations (N), arithmetic mean (Mean), SD, and coefficient of variation (CV%, calculated by $SD/Mean \times 100$), geometric mean and coefficient of variation for geometric mean (CV% Geometric Mean), and median, minimum, and maximum values at each sampling time. The CV% Geometric Mean will be calculated according to a formula $CV\% \text{ Geometric Mean} = [\exp(sd^2)-1]^{1/2} \times 100$, where sd is the standard deviation for natural logarithm (ln)-transformed data. Time course profiles for plasma concentration data will be presented graphically. Based on plasma concentration data on Days 5 and 6 and using non-compartmental methods, the following PK parameters will be calculated, whenever possible, for each patient who completed at least 5 days of study drug administration in the intensive PK sampling group:

C_{\max} (ng/mL): Maximum plasma concentration

T_{\max} (hr): Time to C_{\max}

$AUC_{0-\tau}$ (ng·hr/mL): AUC over the dosing interval τ (ie, 24 hours), calculated by the trapezoidal method (Linear Up/Log Down Trapezoidal Method)

CL/F (L/hr): Apparent total clearance estimated according to:
 $CL/F = Dose/AUC_{0-\tau}$

The estimated PK parameters will be summarised with N, Mean, SD, CV%, geometric mean, CV% Geometric Mean, median, minimum, and maximum values. The T_{\max} will be summarised with N, Mean, SD, CV%, median, minimum, and maximum values.

Specification of the PK parameters for analysis and the level of statistical significance, together with procedures for accounting for missing, unused or spurious data, procedures for reporting deviations from the original statistical plan, and the selection of patients to be included in the analyses population(s) will be presented in the report and/or the PK analysis plan, as appropriate.

PK parameters to be reported will be detailed in the PK analysis plan. Other parameters may be added if appropriate.

Non-compartmental PK calculations will be performed by using WinNonlin Version 6.2.1 or higher.

Population PK and PK/PD analyses will be planned and reported separately.

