1.3 Clinical Studies with of Lusutrombopag (S-888711)

S-888711 is an orally active, small-molecule TPO receptor agonist that acts on the transmembrane domain of human TPO receptors, activates the signal transduction pathway in the same manner as endogenous TPO, and leads to an upregulation of platelet production.

Following single (0.1 to 50 mg) and multiple (once daily for 14 days; 0.25 to 2 mg) dosing, S-888711 increased platelet production in a plasma-exposure dependent manner. Furthermore, S-888711, at the doses and regimens investigated, was safe and well tolerated. The maximum plasma concentration (C_{max}) and the area under the plasma concentration-time curve (AUC) for S-888711 increased dose-proportionally, with plasma S-888711 concentrations reaching steady state within 7 days of the initial dose. Further studies showed that the pharmacokinetics (PK) of S-888711 were unlikely to be affected by food, race, most concomitant drugs, or hepatic function.

Two open-label, phase 2 studies (Studies 1017M0623 and 1112M0625) conducted in Japan were designed to investigate the optimal dose of S-888711, administered once daily for 7 days, in thrombocytopenic patients with CLD who were scheduled to undergo percutaneous liver ablation (including liver coagulation). The efficacy, safety, and PK of S-888711 as a pre-treatment for percutaneous liver ablation were assessed at doses of 0.25, 0.5, 1, 1.5, and 2 mg/day (Study 1017M0623) or 2.5, 3, and 4 mg/day (Study 1112M0625). The data demonstrated that doses of ≥ 2 mg/day were required to increase platelet counts in thrombocytopenic patients to levels above $50 \times 10^9/L$ to perform percutaneous liver ablation.

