5.2 Treatments to be Administered

One S-888711 3 mg tablet or matching placebo tablet will be taken once daily. Study drug will be administered for up to 7 days. On Days 5 to 7, the platelet count must be measured before administration of study drug. If a patient meets the administration stopping criterion (ie, platelet count $\geq 50 \times 10^9/L$ with an increase of $\geq 20 \times 10^9/L$ from baseline), no additional dose of study drug will be administered.

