7.6 Pharmacokinetic Assessment

7.6.1 Drug Concentration Measurement

All patients will undergo blood sampling for the PK assessment of S-888711. At least 20 patients will undergo intensive blood sampling (Table 7-2) and the remaining patients will undergo sparse blood sampling (Table 7-3). The actual time and date of all blood collections will be recorded on the CRF.

Table 7-2: Intensive Blood Sampling

Study Day	Blood Sampling Time	Allowance
Day 5	• Pre-dose	• Within 60 minutes before administration
	• 2 hours after dose	• \pm 15 minutes after dose
	• 4 hours after dose	
	• 6 hours after dose	
	• 8 hours after dose	
Day 6	• 24 hours after Day 5-dose	• \pm 60 minutes after Day 5-dose, but before Day 6-dose
Day 7	• 48 hours after Day 5-dose	• Simultaneous sampling with platelet count determination

Table 7-3: Sparse Blood Sampling

Study Day	Blood Sampling Time	Allowance
Day 5	• Pre-dose	• Within 60 minutes before administration
	• 2 to 4 hours after dose	• Within the specified time window (ie, 2 to 4 hours after dose)
Day 6	• 24 hours after Day 5-dose	• Simultaneous sampling with platelet count determination
Day 7	• 48 hours after Day 5-dose	• Simultaneous sampling with platelet count determination

Blood samples for the PK assessment will be collected by the investigator or designee at the pre-specified time points. All samples will be sent to the central laboratory for processing. Full details of the sample collection, handling, labelling, storage, and shipping procedures will be specified in a separate manual.

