7.9 Withdrawal of Patients from the Study Drug or Study

7.9.1 Withdrawal of Patients from the Study Drug (ie, Study Medication)

The investigator or designee will withdraw a patient from study medication for any of the following reasons:

- Platelet count $\geq 50 \times 10^9/L$, with an increase of $\geq 20 \times 10^9/L$ from baseline (ie, the administration stopping criterion).
- Occurrence of a thrombosis-related AE.
- If a serious or intolerable AE occurs and the investigator believes the patient should be withdrawn from the study medication because of that AE.
- The patient requests to be withdrawn from the study medication.
- The patient is proved to be ineligible for the study after participation in the study has begun.
- The investigator determines that the patient should be withdrawn from the study medication due to other reasons.

Even after withdrawal from study medication, study assessments in the Treatment period (Days 1 to 7) and the Post-treatment period (Days 8 to 35) will be performed on schedule, as specified in the study protocol.

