8.3 Analysis Populations

The following analysis populations are defined:

Intention-to-Treat (ITT) Population will include all randomised patients. Any mis-randomised patients will be analysed according to the treatment randomised to. This population is the primary population for the analysis of efficacy.

Safety Analysis Population will include all randomised patients who actually receive at least 1 dose of the study drug. This population will be analysed according to the treatment that patients actually received, rather than the treatment to which they were randomised. This population is the primary population for the analysis of safety.

Per Protocol (PP) Population will include all randomised patients who have no major protocol deviations pertaining to the efficacy evaluation. This population will be used in a sensitivity analysis.

Pharmacokinetic Concentration Population will include all patients who undergo plasma PK sampling and who have at least one evaluable PK assay result for S-888711. This population will be used for the concentration listing, as well as for plotting the concentration-time data.

Pharmacokinetic Parameter Population will include all patients with at least one PK parameter estimated in the intensive PK sampling group. This population will be used for PK parameter listing and summary.

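### The five-day dosing condition in Protocol 8.12 drops Day 5 responders from the Day 5 pre-dose concentration summary, although that sample depends only on the doses of Days 1 to 4

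*Protocol*

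**What the plan says.** Protocol 8.12 separates listing from summarising. The listing has no dosing requirement: "Plasma S-888711 concentrations will be listed by nominal sampling time and sampling design group". The summary statistics do: "Plasma S-888711 concentrations for patients who completed at least 5 days of study drug administration will be summarised by nominal sampling time". No nominal time is exempted. The same five-day condition applies to C_max, T_max, AUC over the dosing interval and CL/F in the intensive-sampling group.

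Protocol 8.3 defines the Pharmacokinetic Concentration Population by one evaluable assay result, with no minimum dosing, and says of it: "This population will be used for the concentration listing, as well as for plotting the concentration-time data".

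Protocol 5.2 sets the timing of the stopping check: "On Days 5 to 7, the platelet count must be measured before administration of study drug". Once the criterion is met, "no additional dose of study drug will be administered".

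Protocol 7.6.1 says "All patients will undergo blood sampling for the PK assessment of S-888711". Under both the intensive and the sparse scheme the first sample is Day 5 pre-dose. Protocol 7.9.1 adds that after drug is stopped, "study assessments in the Treatment period (Days 1 to 7) and the Post-treatment period (Days 8 to 35) will be performed on schedule".

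On exposure and effect, Protocol 1.3 reports from early single- and multiple-dose work that "S-888711 increased platelet production in a plasma-exposure dependent manner".

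**The concern.** A Day 5 pre-dose concentration is determined by the doses of Days 1 to 4. Whether a Day 5 dose follows cannot change it. Requiring five dosing days for that row therefore removes a usable observation because of something decided after the four doses that produced it, namely an early platelet response.

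If patients with higher exposure tend to respond sooner, the removed troughs would sit in the upper part of the distribution, and the table would describe a slower-responding subset. The plot, drawn from the unrestricted population, could then show different patients from the table at the same time point, with nothing in 8.12 to explain it. Assessing PK is a secondary objective and plasma concentration is a listed secondary endpoint, so the table should describe the dosed population as far as the data allow.

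**Working it through.** The plan states no figure on this point, so there is none to reproduce. The check has two parts.

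**1. Who is removed (from the documents).** The stopping check precedes dosing on Days 5, 6 and 7, so dosing days at stop = day of stop - 1, if no dose was missed.

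| Criterion met on | Dosing days | In the summary table? |
|---|---|---|
| Day 5 | 4 | No |
| Day 6 | 5 | Yes |
| Day 7 | 6 | Yes |
| Not met by Day 7 | 7 | Yes |

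The stopping rule therefore removes Day 5 responders only. Their Day 5 pre-dose sample is scheduled (Protocol 7.6.1, 7.9.1, Appendix 1) and follows the same four doses as everyone else's.

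**2. How far the summarised trough could move (assumptions).** The documents give neither the share of patients stopping on Day 5, nor the variability of the trough, nor the correlation between a patient's trough and Day 5 response. Assume:

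- share stopping on Day 5, p: 2% to 20% (2 to 20 of 100 S-888711 patients);
- coefficient of variation (CV) of the trough: 30% or 50%, with log-scale SD σ = sqrt(ln(1 + CV²)), i.e. 0.294 or 0.472;
- correlation ρ of log trough with a latent response score: 0, 0.3 or 0.6, with the top fraction p of that score removed.

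The ratio of geometric means, kept to all, is exp[-ρ σ φ(z) / (1 - p)], where z is the (1 - p) normal quantile and φ the normal density. Example with p = 20%, ρ = 0.6, CV 50%: z = 0.842 and φ(z) = 0.280, so exp(-0.6 × 0.472 × 0.280 / 0.80) = exp(-0.099) = 0.906.

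| CV, ρ | p = 2% | 5% | 10% | 20% |
|---|---|---|---|---|
| any CV, 0 | 1.000 | 1.000 | 1.000 | 1.000 |
| 30%, 0.3 | 0.996 | 0.990 | 0.983 | 0.970 |
| 30%, 0.6 | 0.991 | 0.981 | 0.966 | 0.940 |
| 50%, 0.3 | 0.993 | 0.985 | 0.973 | 0.952 |
| 50%, 0.6 | 0.986 | 0.970 | 0.946 | 0.906 |

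For the arithmetic mean the ratio is Φ(z - ρσ) / (1 - p). Its lowest value on this grid is 0.890.

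A cruder calculation agrees. If a share p has a mean trough r times that of the rest, the relative bias is -p(r - 1) / [1 + p(r - 1)]. With p = 5%, r = 1.3 it is -0.015/1.015 = -1.5%. With p = 20%, r = 1.5 it is -0.10/1.10 = -9.1%. With r = 1 it is zero.

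**A force in the other direction.** The five-day condition also removes patients who fall below five dosing days through missed doses, and their troughs would be lower. If a share q has troughs at a fraction f of typical, removing them multiplies the geometric mean by f^(-q). That gives 1.007 for q = 2%, f = 0.7 and 1.035 for q = 5%, f = 0.5 (assumed values). This matters if the comparison is with all sampled patients. It does not if the target is patients who took all four doses of Days 1 to 4.

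**The case against.** **The bias is not demonstrated.** A reader might infer that the reported trough is biased low as a fact and that exposure under 3 mg is understated. The documents do not support that. The statement in Protocol 1.3 covers single doses of 0.1 to 50 mg and multiple doses of 0.25 to 2 mg, so it describes a relation across doses. It gives no correlation between one patient's trough and that patient's Day 5 response at a fixed 3 mg. Stopping also depends on baseline count: the rise needed is the larger of 20 and (50 - baseline), so 20 for a baseline of 30 or more but 30 for a baseline of 20 (all × 10⁹/L). This objection stands. The direction is an inference and the size may be zero.

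**No data are lost.** A reader might take the restriction to cover every concentration output. It covers the summary statistics. The listing and plots are unrestricted, and population PK and PK/PD are planned separately. This stands.

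**The rule may be settled elsewhere.** Protocol 8.12 leaves patient selection to the report and/or a PK analysis plan, and SAP section 1 puts PK in a separate document. Neither was available, and the case may be handled there. What 8.12 now states is nevertheless a definite rule, not an omission.

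**The Day 5 window has no anchor.** Its 60-minute allowance is defined relative to a dose that a Day 5 stopper never takes. This stands as a practical detail. Actual sampling times are recorded, so they can be used.

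**One patient set keeps the profile comparable.** This is weak, because the plan already mixes dosing histories. A Day 6 stopper's Day 7 sample comes 48 hours after the last dose, while a patient dosed on Day 6 has a sample about 24 hours after the last dose. Both stay in the table.

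**Sampling error is larger.** With 20 intensive patients split evenly (assumed), about 10 receive active drug, and the standard error of the mean is 30%/√10 = 9.5% to 50%/√10 = 15.8%. That holds for the intensive group only. The roughly 90 active patients sampled sparsely give 30%/√90 = 3.2% to 50%/√90 = 5.3%.

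**Conclusion.** The concern holds in a limited form. As written, the five-day condition with the pre-dose stopping check excludes Day 5 responders from the Day 5 pre-dose summary, although their sample is valid for that row. That is selection on early response and follows from the text alone.

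The consequence is a possible bias in the summarised trough, probably downward if exposure and response are positively related within the 3 mg dose. Its size cannot be determined from the documents. On the assumed grid (2% to 20% stopping on Day 5, correlation 0 to 0.6, CV 30% or 50%) it runs from zero to about -10%: down to -9% for the geometric mean and -11% for the arithmetic mean. At 5% stopping the geometric mean moves by 0 to -3%. Measured against all sampled patients, even the net sign is open, because patients with missed doses also leave the table.

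The effect is confined to descriptive PK. No efficacy or safety test is touched. Excluding Day 5 stoppers from the post-dose Day 5 parameters is unavoidable, because those require a Day 5 dose. This is a cheap improvement, not a threat to the trial's conclusions.

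**What to change.** In Protocol 8.12 and the PK analysis plan:

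- Summarise the Day 5 pre-dose concentration in all patients who took the four doses of Days 1 to 4 and have an evaluable sample, ideally also split by whether dosing stopped on Day 5.
- Keep the five-day condition for samples after the Day 5 dose and for C_max, T_max, AUC and CL/F.
- Beside those results, report how many S-888711 patients were left out because they stopped on Day 5. SAP 7.1 summarises reasons for dosing under seven days, but not by day of stopping.
- State that for Day 5 stoppers the pre-dose sample is placed by its actual sampling time, since there is no dose to anchor the window.

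The cost is a few lines of wording and one changed filter; the samples are already scheduled. The one drawback is that the Day 5 pre-dose row will have a different N from the post-dose rows, so it should be labelled.

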Sampling for plasma drug concentration (Intensive PK) ⁿ							X	X	X															

a Applied to both study medication withdrawn and study assessment withdrawn, except for a patient with drug withdrawn because of the administration stopping criterion (ie, platelet count $\geq 50 \times 10^9/\text{L}$ with an increase of $\geq 20 \times 10^9/\text{L}$ from baseline).

b Only necessary assessments will be performed.

c If platelet count on Day 5, 6 or Day 7 is $\geq 50 \times 10^9/\text{L}$ with an increase of $\geq 20 \times 10^9/\text{L}$ from baseline, a patient must stop taking study medication.

d Confirmed by upper gastrointestinal endoscopy. If data on upper gastrointestinal endoscopy are obtained within 180 days before randomisation, the data can be used.

e Confirmed by ultrasonography, CT, or MRI. If ultrasonography, CT, or MRI is performed within 28 days before randomisation, the image can be used for assessing the presence or absence of splenomegaly.

f Confirmed by ultrasonography, CT, or MRI in the Screening period and after the invasive procedure. The Screening investigation should be arranged as close to randomisation as possible. However, if gastro-oesophageal varices are treated, portal vein thrombosis will be confirmed with the image obtained after the treatment.

g Performed within 3 to 10 days after the invasive procedure. When any additional invasive procedure is performed, the assessment of bleeding events as graded on the WHO Bleeding Scale, portal vein thrombosis, and portal blood flow will be performed before and after the invasive procedure.

h Confirmed by Doppler ultrasonography (at Screening, the investigation should be as close to randomisation as possible).

i Blood samples will be collected before study medication.

j Antithrombin III activity, fibrinogen, fibrin degradation products, D-dimer, Protein C activity, free protein S antigen, von Willebrand factor activity will be performed only at Screening. Prothrombin time (international normalised ratio value) and activated partial thromboplastin time will be performed at Screening, Day 1, Day 8, Day 14, and Day 35.

k Administered after platelet count is confirmed and drug assignment.

l Performed between Days 9 and 14.

m All patients except for Intensive PK; pre-dose, 2 to 4 hours post-dose on Day 5, and pre-dose on Days 6 and 7.

n At least 20 patients; pre-dose, 2, 4, 6, 8 hours post-dose on Day 5, pre-dose on Days 6 and 7.

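### The Day 7 plasma concentration row pools samples taken 24 hours and 48 hours after the last dose, because protocol 8.12 groups by nominal time and not by whether the Day 6 dose was taken

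*Protocol*

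**What the plan says.** Protocol 8.12 states that plasma concentrations "for patients who completed at least 5 days of study drug administration will be summarised by nominal sampling time" and by sampling design. It asks for the mean, SD, CV%, geometric mean and its CV%, median and range at each time, and for time-course plots.

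Tables 7-2 and 7-3 in protocol 7.6.1 give the Day 7 sample the nominal time "48 hours after Day 5-dose" in both sampling groups. Appendix 1 of the protocol, in notes m and n, describes the same sample differently: "pre-dose on Days 6 and 7". The SAP's Appendix 1 repeats those notes.

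On dosing, protocol 5.2 says: "On Days 5 to 7, the platelet count must be measured before administration of study drug". Once the stopping criterion is met, "no additional dose of study drug will be administered". Protocol 7.9.1 adds that after a patient leaves study medication, "study assessments in the Treatment period (Days 1 to 7) and the Post-treatment period (Days 8 to 35) will be performed on schedule". PK sampling is not excepted.

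The PK parameters have a narrower base: "Based on plasma concentration data on Days 5 and 6 and using non-compartmental methods".

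**The concern.** The five-day filter seems meant to make dosing history uniform. It does so for the Day 5 and Day 6 samples, but not for Day 7, because by then some included patients have had a sixth dose and others have not. A label that counts from the Day 5 dose hides the difference, and the pre-dose label in Appendix 1 invites the reader to treat the whole row as a 24-hour trough.

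The mix is not random. Patients lack the Day 6 dose mostly because their platelet count met the stopping criterion; any other Day 6 withdrawal joins them. The Day 7 summary therefore depends on the proportion of early responders in each sampling group. Plasma concentration is a listed secondary endpoint (protocol 8.9.2). At stake are the Day 7 descriptive statistics and the Day 7 point on the time-course plot.

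**Working it through.** **Time since last dose at the Day 7 sample.** The plan states no figure to reproduce, so the first step is to trace the dosing rules in protocol 5.2 against the filter in 8.12.

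| Patient | Doses before Day 7 sample | Passes five-day filter | Time since last dose |
|---|---|---|---|
| Stopped on Day 5 count | 4 | No | not summarised |
| Stopped on Day 6 count | 5 | Yes | 48 h |
| Stopped on Day 7 count | 6 | Yes | 24 h |
| Never stopped | 6 | Yes | 24 h |

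The last three lines share one nominal time. On Day 6, by contrast, every included patient is 24 h after the Day 5 dose, so that row is uniform.

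**Illustrative size.** Inputs:

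- Half-life h: not in the documents. Protocol 1.3 reports steady state within 7 days. Taking four half-lives to steady state gives an upper value of 7 × 24 / 4 = 42 h. The lower value of 12 h is an assumption.
- Fraction f of summarised patients stopped on Day 6: not in the documents; 5%, 10% and 20% are assumed.
- Both groups are assumed to have the same underlying exposure, with one-compartment linear kinetics and doses every 24 h.

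With r = 2^(−24/h), the Day 7 level after six doses is proportional to A = r + r² + … + r⁶. Without the Day 6 dose it is B = r² + … + r⁶. Hence B/A = r(1 − r⁵)/(1 − r⁶).

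- h = 12: r = 0.25, B/A = 0.25 × 0.99902/0.99976 = 0.250
- h = 24: r = 0.5, B/A = 0.5 × 0.96875/0.98438 = 0.492
- h = 42: r = 0.67295, B/A = 0.67295 × 0.86199/0.90713 = 0.639

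Relative to the 24-hour trough, the pooled geometric mean is low by 1 − (B/A)^f and the pooled arithmetic mean by f(1 − B/A).

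| f | Geometric mean low by: h = 12 / 24 / 42 | Arithmetic mean low by: h = 12 / 24 / 42 |
|---|---|---|
| 5% | 6.7% / 3.5% / 2.2% | 3.8% / 2.5% / 1.8% |
| 10% | 13.0% / 6.8% / 4.4% | 7.5% / 5.1% / 3.6% |
| 20% | 24.2% / 13.2% / 8.6% | 15.0% / 10.2% / 7.2% |

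Example: f = 10%, h = 12 gives 1 − 0.250^0.1 = 13.0%.

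**Intensive group.** Protocol 7.6.1 asks for at least 20 patients. Under 1:1 randomisation about 10 would be on active drug, so a single Day 6 stop would make f about 10% in that row.

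**The case against.** Several limits on the point are sound.

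A reader might infer that the reported Day 7 concentrations are wrong. The documents do not support that. Each value is a genuine measurement, and the nominal label in Tables 7-2 and 7-3 is literally true whether or not the Day 6 dose was taken. The difficulty arises when the pooled statistic is read as a trough.

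A reader might also infer that the pooling would make lower exposure appear to go with better response. The row cannot show that, because 8.12 does not split it by response or stopping day. PK/PD analyses are to be planned and reported separately, and nothing says that they will use this row.

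The size is uncertain in both directions. Protocol 3.2 expects the adequate platelet rise in Days 9 to 14, so Day 6 stops may be few. Protocol 1.3 describes platelet production as dependent on exposure, so early responders may start from higher concentrations, which would offset some of the shortfall. Full offset would need underlying exposure about 1/0.639 = 1.6 to 1/0.250 = 4.0 times that of the others. Even then the row would combine two different times after dosing.

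Finally, protocol 8.12 defers data-handling procedures and patient selection to the report or the PK analysis plan, and SAP section 1 places PK in a separate document. That plan was not supplied and may already deal with this. But the deferral concerns missing, unused or spurious data. These samples are valid and on schedule, and 8.12 states its own summary rule outright. The deferral therefore does not clearly cover them.

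**Conclusion.** The point holds, with a narrow reach. As written, the Day 7 descriptive statistics in both sampling groups mix two times after dosing, in proportions set mainly by the platelet stopping criterion, and so have no clear meaning. That much follows from the dosing, sampling and summary rules and needs no assumption about kinetics.

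The size does rest on assumptions. For a half-life of 12 to 42 h and equal underlying exposure, the 48-hour level is about 25% to 64% of the 24-hour trough. With 10% of summarised patients stopped on Day 6, the pooled geometric mean is about 4% to 13% below that trough. These figures illustrate the possible scale; they do not predict it.

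Cmax, Tmax, AUC and CL/F rest on Days 5 and 6 and are untouched. The Day 6 row is sound. Concentration is outside the gatekeeping sequence, so no efficacy test is affected.

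**What to change.** In protocol 8.12 and the PK analysis plan, present the Day 7 sample in two rows within each sampling group: Day 6 dose taken (24 h after the last dose) and Day 6 dose not taken (48 h after the last dose). Plot them separately or plot only the first. Where the 48-hour row holds very few patients, as is likely in the intensive group, list the values and do not summarise them.

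Reconcile the Day 7 label in Tables 7-2 and 7-3 with notes m and n of Appendix 1 in the protocol, and with the same notes in the SAP, so that one description applies to patients with and without a Day 6 dose.

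The cost is a sentence and one table row per sampling group. No new data are needed: actual sampling times (7.6.1) and dosing dates (5.9) are already recorded on the CRF. The downside is fewer patients per row. If the PK analysis plan already makes this split, a cross-reference from 8.12 and the label change are enough.
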